7.2 Days -30 to -1 before the operation

The following information needed to be collected and recorded:

1. Demographic information and medical history of a subject before the operation: including patient age, gender, height, weight, preoperative diagnosis; past medical history, personal history; preoperative laboratory examination results: including white blood cells, red blood cell count, neutrophilic granulocyte count, hemoglobin content, platelet count, alanine aminotransferase (ALT), aspartate aminotransferase (AST), C-reactive protein, albumin, blood glucose, APTT, PT, and INR. If there were multiple laboratory tests before the operation, the latest results should be collected.

2. Concomitant medication: Only the administration of antibiotics within seven days prior to the operation was recorded.

7.3 Operation period (Day 0, the day of operation):

The following information needed to be collected and recorded:

1. Operation: surgeon, surgical procedure, start and stop time of the operation, blood loss during the operation, intraoperative complications, intraoperative shunt, and combined treatment;

2. Record of devices used during the operation: type, No. and batch No. of the cerebral ventricular shunt catheter; type, No. and batch No. of the pressure regulating valve; and type, No. and batch No. of shunt catheters at the abdominal cavity/the lumbar cistern/ the atria.

7.4 Postoperative follow-up period: Days 1-365

An adverse event (except an anticipated adverse event) discovered during the review of postoperative history or hospital database (if any) should be recorded:

The time, description, concomitant therapy, and outcome of an adverse event, information related to the operation and the product, if the implanted part was taken out due to an adverse event, and concomitant medication and treatment should be recorded.

Additional records were required for the following special adverse events:

1. Infection: Infection site which is usually classified into intracranial, skin, and abdominal infections. For intracranial infection, time of infection, white blood cell count, red blood cell count, neutrophilic granulocyte count, hemoglobin content, alanine aminotransferase (ALT), aspartate aminotransferase (AST), C-reactive protein, blood glucose, traits and color of CSF, cell count, Pan's test results, contents of protein, sugar, and chloride in CSF, bacterial culture type, and bacterial susceptibility to rifampicin and clindamycin should be recorded. For skin infection and abdominal infection: white blood cell count, red blood cell count, neutrophilic granulocyte count, bacterial culture type, and bacterial susceptibility to rifampicin and clindamycin should be recorded.

2. Obstruction of catheter: site, reason (judged by an investigator), and nature of obstruction should be recorded.

3. Leakage of CSF: time and position of leakage should be recorded.

4. Mechanical failure: type of mechanical failure should be recorded, including falling out, displacement, twisting, and rupture.

A patient who died within one year was still considered as a complete case. The form of SAE should be completed. And the death should be specified in this study endpoint table.

8 Adverse Event Reporting

8.1 Adverse events

8.1.1 Adverse events

Adverse event (AE) refers to any adverse medical event of a subject, no matter if it is related to this study or a research-related device.

During the assessment of a subject enrolled to this clinical study, an investigator should each time determine whether there was an AE and collect information, including date, severity, treatment, prognosis, and analysis of the AE, and research-related device, operation, or drug, in as detailed a way as possible.

Information of all AEs, research-related device failures, and other product issues should be as much as possible collected from existing medical records, and entered into CRFs.

8.1.2 Anticipated operation-related adverse events

Anticipated AE refers to an event that occurred after the operation during hospitalization (relative to the baseline change of a subject), which was an anticipated consequence of the operation. If an anticipated AE occurred, it would not be reported to the sponsor.

Currently, postoperative anticipated AEs known include:

- Wound pain within 48 hours followed by agitation
- Fever lower than 38.5°C within 48h
- Abdominal distension and constipation within 48h
- A small amount of wound exudation within 48h
- Mild anemia (hemoglobin > 90g/L)
- Increase in white blood cells within 48h

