Inclusion Criteria:	
Subjects who met all of the following inclusion criteria would be enrolled:
 
 1. The informed consent was exempted by the Ethics Committee of a research center. Either a subject or his/her legal representative signed the informed consent form (ICF) prior to enrollment. 2. A subject had an indication suitable to use Bactiseal Catheter. 3. A subject received a hydrocephalus shunt at least one year ago.
Exclusion Criteria:	Subjects who met any of the following exclusion criterion were excluded:

	
1. A subject didn't have an indication suitable to use the product.2. A subject was known to be allergic to a component or ingredient of the product to be implanted, including silicone tubing, rifampicin, and clindamycin.3. According to the comprehensive judgment of an investigator, a subject had an infection of the implant site when the shunt was implanted, such as ventriculitis, meningitis, peritonitis, and local implant skin infection.4. A subject was simultaneously implanted with another shunt system different from Bactiseal Catheter.5. A subject had a contraindication of the shunt operation.6. A subject had uncorrected coagulopathy or any bleeding disorder.
Endpoint	
1. Non-infection rate of a subject within one year2. Type and incidence of adverse events of a subject within one year

Time and Data Collection Form

	Screening	Preoperative	Operation	Postoperative follow-up
Time of data collection	NA	-30 to -1 days	0	Days 1-365
Signed the ICF (if applicable) ¹	X			
Review of inclusion and exclusion criteria	X			
Medical History		X		
Laboratory examination		X		X+
Operative process			X	
Device application record			X	
Adverse events ²			X*	X*
Serious Adverse Events			X*	X*
End of study/exit			X	X
Record of concomitant medication ³		X*	X*	X*
Record of concomitant treatment ⁴			X*	X*

+	Suspicious or proven infection
*	If any

Notes: 1. The ICF (if applicable) needed to be completed before screening.

2. A postoperative anticipated adverse event was not counted as an adverse event.

3. Only antibiotics and medications related to postoperative adverse events were recorded. Only the administration of antibiotics within seven days prior to the operation was recorded.

4. Only the treatment and operation associated with postoperative adverse events were recorded.

Abbreviations:

AE	Adverse events
CRF	Case Record Form
CV	Curriculum Vitae

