3.2 Purpose

This study aimed to collect safety information from subjects implanted with a catheter (trade name: Bactiseal) produced by Codman & Shurtleff, Inc. of the United States. Device safety would be assessed based on all the adverse events that occurred within one year after the subjects were implanted with the catheter.

4. Research Design

This study was designed to be single arm, multi-center, and retrospective.

This is continued access study to enroll additional 50 new subjects, with total combined 150 subjects. The historical study is DPS-201501.

It would collect information on adverse events of subjects enrolled within one year after the implantation of Bactiseal Catheter from August 07, 2018 to August 31, 2019, through case review or hospital database (if any).

The following information would be collected from subjects' medical records:

1. General condition of the subjects
2. Intraoperative condition and catheter implantation
3. Information on the shunt product
4. Adverse events of subjects within one year after the operation and classification of the adverse events
5. Relevant examinations in case of postoperative infection
6. Other adverse event-related information (except anticipated adverse events)

Information on adverse events would be collected. And the safety of clinical application of the product would be assessed.

5. Endpoint

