5.1 Endpoint

1. Non-infection rate of a subject within one year
2. Type and incidence of adverse events within one year of a subject

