10.4 Criteria of qualification/disqualification of the trial results

This study aimed to collect post-marketing safety data on the Chinese population implanted Bactiseal Catheter, according to product registration requirements. It described the occurrence, type, severity, frequency of all AEs occurring during the research, as well as the correlation between AEs and the product. Hence, criteria of qualification/disqualification were not applicable.

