11.4 Data Collection and Management Responsibilities

Data collection is the responsibility of the clinical trial staff at the site under the supervision of the site Investigator. The Investigator is responsible for ensuring the accuracy, completeness, legibility, and timeliness of the data reported.

The recruitment of the study centers and the extraction of data from patients' medical records will be closely monitored to reach the proposed sample sizes. The study investigators will be asked to extract the data from the medical records of all patients implanted with Hakim programmable shunt system for the study in their respective centers. Integra Clinical Operations will follow up with the centers during the data collection process when appropriate to ensure a rapid completion of the data collection process.

Hardcopies of the study visit CRFs will be provided for use to collect data for each subject enrolled in the study. Data recorded in the CRFs derived from any source documents should be consistent with the data recorded on those source documents.

Clinical data (including AEs), concomitant medications, and expected adverse reactions data) and clinical laboratory data will be entered into Microsoft Access Database by Sponsor by double data entry. The data will be reviewed and validated. Queries for any missing, inconsistent or illogical data points will be forwarded to the research center for resolution. After all data queries are resolved, the data will be transferred to a biostatistician for analysis.

12 Ethical and Regulatory Requirements

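### The plan promises an assessment of all adverse events within one year, but removes anticipated events under a broad, apparently open definition, so the any-AE incidence is mislabelled

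*Combined protocol and SAP*

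**What the plan says.** **Text that promises all events.** Section 3.2 states: "Device safety would be assessed based on all the adverse events that occurred within one year after the subjects were implanted with the catheter". The Summary states the same purpose. The endpoint in 5.1 is "Type and incidence of adverse events within one year of a subject", with no exception. Section 8.1.1 defines the term without limit: "Adverse event (AE) refers to any adverse medical event of a subject, no matter if it is related to this study or a research-related device". It goes on: "Information of all AEs, research-related device failures, and other product issues should be as much as possible collected from existing medical records". Section 10.4 says of the study: "It described the occurrence, type, severity, frequency of all AEs occurring during the research".

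**Text that removes anticipated events.** Section 8.1.2 defines them as in-hospital postoperative changes from baseline that are an expected result of surgery, and rules: "If an anticipated AE occurred, it would not be reported to the sponsor". Note 2 to the Time and Data Collection Form says: "A postoperative anticipated adverse event was not counted as an adverse event". Section 7.4 excepts them from what is recorded during follow-up, and 8.5 excepts them from what is reported.

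**Partial disclosure.** The Summary and section 4 mention the exception in item 6 (other AE-related information). Item 4, which covers adverse events within one year and their classification, carries none.

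**Serious events.** Section 8.3 defines SAEs as a subset of adverse events, and one criterion is a longer hospital stay. Section 8.5 requires investigators to report SAEs to the sponsor within 24 h and attaches no anticipated-event exception to that sentence.

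**The concern.** Two instructions about the same events cannot both be followed. An investigator working from 8.1.1 enters a low postoperative fever as an AE. One working from 7.4 or note 2 does not. The AE incidence then depends on which section was read.

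The boundary of the exclusion is also soft. The list in 8.1.2 is introduced as what is currently known to be included, so other in-hospital events judged to be expected results of surgery could be added at the abstractor's discretion. Nothing says what happens when a listed sign meets a seriousness criterion in 8.3. Nor does anything say what happens when it proves to be part of an infection or of a complication named in 5.2 and 10.1. Low fever, wound exudation, raised white cells and abdominal distension are all signs for which that question can arise.

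Monitoring would not necessarily show the difference. The 100% source check in 11.3.2 covers events that met the AE reporting criteria, and an event classed as anticipated does not meet them.

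Under 10.7 the report goes to NMPA in support of extending the product registration. A table said to cover all AEs would there describe something narrower.

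**Working it through.** The plan gives no AE rate, so there is no AE figure to reproduce. Its only computed figures concern the non-infection endpoint (10.3):

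- N(1) = 150 × e^−(0.044 + 0.1) = 129.88, stated as 130. With 0.043, the rate given in the text, it is 130.01.
- Margin = 1.96 × √(0.957² × 0.043 / 130) = 3.41%, stated as 3.4%.

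Both reproduce. Infection is not among the anticipated events, so this point does not change them.

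**Step 1: which text governs.**

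| Question | All events | Anticipated events out |
|---|---|---|
| Is it an AE? | 8.1.1: yes | Note 2: not counted |
| Is it recorded? | 8.1.1: yes, as far as possible | 7.4: excepted |
| Is it reported to the sponsor? | 8.1.1: entered in the CRF, the reporting route in 8.5 | 8.1.2 and 8.5: excepted |
| Is it described in the results? | 3.2, 5.1, 10.4: yes | Not possible if never recorded |

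No passage says which column takes precedence.

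**Step 2: direction for the any-AE incidence.** Let A be the subjects with at least one non-anticipated AE, B those with at least one anticipated event, and N the number analysed.

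- Under the 8.1.1 definition: incidence = |A ∪ B| / N.
- Under the exclusion: incidence = |A| / N.
- Difference = |B not in A| / N, the share of subjects whose only events were anticipated.

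This is never negative, and it is positive as soon as one such subject exists. Each one is worth 1/50 = 2.0 points among the new subjects, or 1/150 = 0.67 points in the combined 150. The documents do not say how many there would be. Event counts fall with every anticipated event, including those in subjects who also have another AE.

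**Step 3: serious events.** Take a listed sign that extends the hospital stay.

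- By 8.5, it meets an 8.3 criterion, so it is reported as an SAE. Shortfall: zero.
- By note 2 with 8.3, it is not an AE and so cannot belong to a subset of AEs. Shortfall: the share of subjects whose only serious event was classed as anticipated.

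The text supports both routes. In the collection table, note 2 is attached to the Adverse events row and not to the separate Serious Adverse Events row, which favours the first.

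**Step 4: limits already on the list.** Of six items, five stop at 48 h. Fever (below 38.5 °C), wound exudation (a small amount) and anaemia (mild, haemoglobin above 90 g/L) carry severity limits. Anaemia has no 48 h limit but is confined to the hospital stay by the definition. These limits bound the listed items. They do not close the list, and none of them is a rule on seriousness or on a later diagnosis.

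**The case against.** The strongest reply is that note 2 defines the term. If an anticipated event is not an AE, then all AEs means all the rest and nothing is inconsistent. That would work if the plan had one definition. But 8.1.1 gives a different and wider one, and 8.1.2 and 8.5 themselves call these events adverse events before excepting them. A table footnote does not settle that.

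Second, the exclusion is stated openly in several places, and leaving minor expected postoperative signs out of a device registry is a legitimate choice. This stands. The fault lies in the label and the boundary, not in having an exclusion.

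Third, a reader might infer that SAE rates are understated by design. The documents do not support that. Section 8.5 requires SAEs to be reported without exception, note 2 is not on the SAE row, 7.4 requires an SAE form for every death, and the listed events are mostly mild and brief. What remains is the conflict in Step 3.

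Other tempting inferences are also too strong:

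- **Lost infection dates.** A sign that proves to be infection is not naturally an expected result of surgery, and 7.4 asks for the time of each recorded AE and of intracranial infection.
- **Irrecoverable data.** Section 11.3.4 keeps source records for at least 10 years.
- **Section 11.4.** It lists "expected adverse reactions data" among the data to be entered, but that is not the defined term, and the same section names a different shunt product, so it may be carried-over text.

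A time limit for the anaemia item and tick-boxes on the CRF would be preferences. The point does not depend on them.

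**Conclusion.** The point holds for the any-AE incidence and for its description. Followed as written, the exclusions give an incidence lower than the plan's own AE definition would give, by the share of subjects whose only events were anticipated. The direction follows from the definitions. It assumes only that abstractors apply 7.4, 8.1.2, 8.5 and note 2, and that at least one such subject exists. The size cannot be estimated from the documents.

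For SAEs the finding is an unreconciled conflict between 8.3 with note 2 and the reporting duty in 8.5, not a demonstrated shortfall. The one-year non-infection rate and its margin are not directly affected, and the complications listed in 10.1 are not on the anticipated list. The change should be made because the result goes to a regulator as a description of all AEs and the correction is inexpensive.

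**What to change.** 1. Reconcile note 2, 7.4, 8.1.2, 8.3 and 8.5. Make the anticipated list closed, so that only the named items can be excluded.
2. In the same sections, state that any event meeting 8.3, or forming part of an infection or of a 5.2/10.1 event, is always recorded as an AE or SAE, even if it first appeared as a listed sign.
3. In the Summary, 3.2, 5.1 and 10.4, restate the scope as all adverse events other than the listed anticipated events, and label the AE tables in the report the same way.
4. When the 100 subjects from DPS-201501 are pooled with the 50 new ones, state which exclusion rule was used for the historical data. The documents do not give it, and a difference would make the two parts of a pooled AE rate non-comparable.

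The cost is wording in the sections named. The reported AE count may be slightly higher, because events at the boundary now stay in. The sample size and the infection analysis do not change.

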8.2 Unanticipated adverse device effect

Unanticipated adverse device effect (UADE) refers to a serious adverse effect, a life-threatening issue, or death caused by or related to the devices, or a serious and unanticipated issue related to the rights, safety, or health of a subject and the devices. In addition, the nature, severity, or frequency of such an event was not specified in the study proposal, IFU, and clinical trial instructions.

8.3 Serious Adverse Events

Serious adverse event (SAE) refers to any of the following adverse events:

- 1) Cause Death,
- 2) Serious deterioration of a subject's health, including:
 - a. A life-threatening illness or injury,
 - b. Permanent damage of the body structure or a body function,
 - c. Hospitalization or extension of the current hospital stay:
 - d. Medical or surgical intervention required to avoid a life-threatening disease or prevent permanent damage to the body structure or a body function,
- 3) Fetal distress, fetal death, congenital malformation, or birth defects.

In this retrospective study, planned hospitalization or medical intervention due to a disease existing before the operation not followed by serious deterioration of health was not regarded as a serious adverse event.

8.4 Duration of follow-up after an adverse event

As this is a retrospective study, it did not intervene in subjects' normal treatment. Therefore, all adverse events were properly dealt with by an investigator based on medical requirements. And no additional

Proposal No.: C-BSEAL-001
Date of proposal: V1.0/2019-11-18
follow-up would be performed.

8.5 Adverse event reporting

Within one year after the shunt operation of a subject, all the adverse events (except anticipated adverse events) recorded in the medical records or hospital database (if any) should be reported. An investigator reported AEs to the sponsor via CRF.

An investigator should record the nature, severity, treatment and prognosis of an AE and determine the correlation with the devices, medication, or operation involved in this clinical study.

An investigator must report SAEs and UADEs to the sponsor (or a designated person) within 24h after their occurrence, and report them to the Ethics Committee in a timely manner. In the event of any request by the sponsor, additional information should be provided. The investigator should judge the time associated with the research product. The research center should report them to a local medical device adverse event monitoring organization. Death should be reported within 7 days, after it was known. A serious injury or an event that might result in death or a serious injury should be reported within 20 days after it was known. The sponsor would report to NMPA and/or a local medical device adverse event monitoring organization in line with the same requirements as those of the research center. If the adverse event had existed or been reported in the previous reporting system, it would be unnecessary to report it repeatedly.

The sponsor should regularly inform all the clinical investigators of this study of all SAEs and UADEs.

8.5.1 Severity criteria

The severity of an adverse event could be classified as mild, moderate, and severe according to the following criteria.

- Mild: It was transient and mild with no influence on daily life, and no special measures or treatment was required.
- Moderate: It had a slight impact on daily life. Measures or treatments were needed, if necessary.
- Severe: It had a serious impact on daily life. Special measures or treatment must be taken, and hospitalization was required, if necessary.

8.5.2 Determination of causal relationship

The relevance between any adverse event and a research-related device should be judged, according to the following criteria, including unrelated, possibly unrelated, possibly related, probably related, and definitely related. If an AE was judged to be possibly related, probably related, or definitely related to a research-related device, such an AE was related to the devices.

- Unrelated: An AE was not related to the devices.
- Possibly unrelated: An adverse event was more likely to be related to other factors, such as concomitant medication or disease. Or the timing of the AE indicated that it was unlikely to be caused by a research-related device.
- Possibly related: An AE might be caused by a research-related device. Other reasons were not excluded, such as concomitant medication or disease. When the occurrence of an AE and the use of a research-related device had a reasonable time sequence, the causal relationship between the

event and a research-related device could not be excluded.

- Probably related: An AE was probably caused by a research-related device. An AE and the use of a research-related device had a reasonable time sequence. For example, the causal relationship was proved after the device was taken out. There was unlikely to be another explanation, such as concomitant medication or disease.
- Definitely related: The type of an AE was identified as a side effect of a research-related device, which could not be explained by other reasons, such as concomitant medication and disease. The time of an AE strongly implied a causal relationship (e.g. reaction after the removal and re-implantation of a device).

9 Early Termination of the Study

